1.1 Study design

This is a prospective, single-arm, open-label, multicenter study to evaluate the efficacy and safety of brolucizumab 6 mg in patients with nAMD.

Patients will be required to attend 6 mandatory study visits: Screening/Baseline Visit (Day 1), Week 4, Week 8, Week 12, Week 16 and Week 48 visits. The timing of the interim visits between Week 16 and Week 48 will depend on the patient's injection regimen, i.e. q12w or q8w.

[figure not shown]
Planned number of patients

Approximately 210 adult patients will be screened and included (10% dropout rate and uninterpretable images at Baseline and Week 12 are expected) in France. The maximum study duration for 1 patient is 48 weeks, including Screening.

There will be 2 periods in this study (see Figure 1-1):

- Open-label treatment period: from Screening/Baseline (Day 1) to Week 40/Week 44 (depending on assigned regimen)
- Follow-up period: Week 40/Week 44 to Week 48

Figure 1-1 Study design

^{*} Week 40 or Week 44 according to treatment schedule

Patients will receive 3 initial doses every 4 weeks ((Day 1, Week 4 and Week 8) loading phase), which should be at least 21 days apart, followed by treatment q12w with the possibility of adjusting to treatment q8w based on disease activity.

Disease activity will be assessed based on investigator's judgment of visual acuity and anatomical parameters as provided in the guidance to the investigators, e.g. decrease of visual acuity and/or other signs of the disease (e.g. intraretinal fluid (IRF), subretinal fluid (SRF), sub-retinal pigmented epithelium (sub-RPE) fluid, retinal hemorrhage, central retinal thickness (CRT) increase, etc.). Disease activity will be assessed during the first q12w interval at Week 16. If no disease activity is observed by the investigator in the study eye, disease activity will be assessed every 12 weeks (at Week 20, Week 32 and Week 44). If disease activity is observed by the investigator in the study eye at any of these visits, the study treatment will be adjusted by the investigator to a q8w treatment regimen and will remain on this regimen until Week 40/Week 44. Patients who require study treatment every 4 weeks after the initiation phase will be discontinued from further study treatment at the next visit.

^{**} End of study visit: 4 or 8 weeks after the last IVT, depending on the last IVT date

1.2 Study objectives and endpoints

Table 1-1 Objectives and related endpoints

Objectives	Endpoints	
Primary objectives	Endpoints for primary objectives	
To evaluate the short-term effect of brolucizumab on CNV lesion area as measured by OCT-A in nAMD patients.	Percentage change in CNV lesion area measured by OCT-A from Baseline to Week 12.	
Secondary objectives	Endpoints for secondary objectives	
To evaluate the long-term effects of brolucizumab on CNV morphology as measured by OCT-A in nAMD patients.	Percentage change in CNV lesion area measured by OCT-A from Baseline to Week 48.	
	Change in OCT-A features assessed by qualitative and quantitative criteria from Baseline by visit at Week 12 up to Week 48.	
To evaluate the effect of brolucizumab on anatomical parameters as assessed by SD- OCT and FA from Week 12 up to Week 48.	• Change in SD-OCT and FA features assessed by qualitative and quantitative criteria (e.g. CSFT, sub- and/or intraretinal fluid, sub-RPE fluid) from Baseline by visit up to Week 48.	
To evaluate the efficacy of brolucizumab up to Week 48 by assessing changes in BCVA.	Change in BCVA from Baseline up to Week 48.	
To estimate the proportion of patients treated at q12w frequency with brolucizumab.	• Proportion of patients who are maintained on an exclusive q12w interval following the loading phase through to Week 48.	
To estimate the predictive value of the first q12w cycle for maintenance of q12w treatment with brolucizumab.	• The probability of the first q12w interval for determining successful q12w maintenance at Week 48.	
To evaluate the time from last IVT injection in the initiation phase to first visit with no disease activity.	Time from last IVT injection in the initiation phase to first visit with no disease activity.	
To evaluate the safety of brolucizumab.	Incidence of AEs (serious and non-serious) reported in patients treated with brolucizumab.	

AEs= adverse events, BCVA= best corrected visual acuity, CNV= choroidal neovascularization, CSFT= central sub-field retinal thickness, FA= fluorescein angiography, IVT= intravitreal nAMD= neovascular age-related macular degeneration, OCT-A= optical coherence tomography-angiography, SD-OCT= spectral domain optical coherence tomography, sub-RPE= subretinal pigmented epithelium

2 Statistical methods

2.1 Data analysis general information

Patients who consent and meet all the inclusion and none of the exclusion criteria will be screened to evaluate eligibility. After confirmation of eligibility, patients will be included and treated with brolucizumab 6 mg and data will be analyzed.

All categorical data will be presented in terms of frequencies and percentages. Summaries of continuous data will be presented in terms of n (the number of non-missing data points), mean, standard deviation (SD), median, lower and upper quartiles, minimum, maximum and the number of missing data points.

For descriptive statistics, the following rules for number of decimal places will be applied: arithmetic mean, median, lower quartile and upper quartile to 1 more decimal places than the raw data; minimum and maximum to the same number of decimal places as the raw data and SD to 2 more decimal places than the raw data. Percentages will be presented to 1 decimal place.

2.1.1 General definitions

Study treatment: This is a single-arm study and all patients will be treated with brolucizumab 6 mg. Three loading injections (at Screening/Baseline/Day 1, Week 4 and Week 8), followed by maintenance treatment from Week 16/Week 20 up to Week 40/Week 44. The investigator can individualize treatment intervals depending on disease activity, to adjust patient's injection regimen.

Study treatment start and end date: Study treatment start date is defined as the first date study treatment is administered and recorded on the treatment administration record (DAR) electronic case report form (eCRF) page. Similarly, study treatment end date is defined as the last date of study treatment is administered and recorded on the study treatment completion CRF page.

Generally, study day 1 is considered as the day of inclusion of the patient. However in this study, treatment is intended to be administered on the same day or if this is not possible, within 3 days after the day of inclusion of the patient.

Study day will be calculated as (event date – study treatment start date + 1 day) for events that occurred on or after study treatment start date (e.g. visit, AEs). For events prior to study treatment start date (e.g. time since diagnosis), study day will be negative and calculated as (event date – study treatment start date).

Baseline and post-baseline: Baseline value refers to the value of the last non-missing measurement collected prior to administration of the first dose of study treatment (Screening or Baseline visit). Intraocular pressure (IOP) will be assessed in the study eye, pre-dose and post-dose at every injection. The last available assessment taken prior to the first IVT injection of study treatment is taken as the "Baseline" assessment.

A "post-baseline" value refers to a measurement taken after the first dose of study treatment. When assessments and treatments take place on the same day, treatment must occur after completion of the efficacy assessments and pre-injection safety measures (tonometry, slit lamp and fundus examinations). If study visit assessments and the corresponding treatment occur on separate days, a repeat safety check-up will be performed prior to treatment of the eye and

results documented in the source documents. More post-baseline safety measurements will be recorded in source document; visit window will be applied to OCT and IVT visits.

Change from Baseline: The difference of measure between post-baseline and Baseline is called change from Baseline.

Percent change from Baseline: The percent change from Baseline will be calculated as below: ((post-baseline value – Baseline value) /Baseline value)*100.

On-treatment period: The on-treatment period lasts from the date of first administration of study treatment to 28 days after the date of the last actual administration of any study treatment.

Treatment duration: The maximum planned duration of treatment for each patient is 40 to 44 weeks in accordance with the designated treatment regimen. Discontinuation of study treatment for a patient occurs when study treatment is stopped earlier than the protocol planned duration and can be initiated by either the patient or the investigator.

Treatment discontinuation: When patients discontinue study treatment but continue in the study, the efficacy data will be used at the time the patient stopped study treatment.

Dry retina: Absence of fluid (IRF/SRF/sub-RPE) will be considered as dry retina.

Event for maintenance q12w interval: In case the investigator selects q12w interval for a patient and the patient maintains the q12w interval until the first q8w interval has started then this will be considered as an event. In case the investigator maintains q12w interval (does not select q8w interval at any time in study) until EOS or patients got early discontinuation from study then patients will be considered as censored.

Event for no disease activity: When patients will be with no disease status as per investigator decision after last dose in initiation phase then the patients will consider as event for disease activity. If patients with active disease status or early discontinue then patients will be considered as censored for disease activity.

Event for dry retina: When patients have absence of fluid then it will be considered as an event of dry retina. If patients have a presence of fluid before/at EOS or early discontinuation then will be censored.

Maximum duration of dry retina: The longest consecutive interval of dryness will be considered as maximum duration of dryness. This duration will be obtained from end date of dryness and start date of dryness for longest interval. If subjects obtain dryness at end of study then duration will be obtained from end of treatment.

Study eye and fellow eye: The investigator selects the eye with the worse BCVA at Screening as the study eye. Otherwise, the investigator deems as a study eye more appropriate to select the eye with better BCVA, based on medical reasons or local ethical requirements. If both eyes are eligible as per the inclusion and exclusion criteria, then it is recommended to select the right eye as the study eye.

The fellow eye will be examined only at Screening/Baseline and Week 48/EOS visits. Only best corrected near visual acuity (BCNVA) for the fellow eye will be analyzed. It is not requested for the purpose of this study to do any self-assessment measure of the fellow eye.

CNV lesion area

A new angiography tool, namely optical coherence tomography-angiography (OCT-A) is a dye-less angiographic procedure based on split-spectrum-decorrelation-amplitude angiography that has become an essential and widely used tool, particularly for imaging CNV and vascular diseases of the retina. The literature suggests that OCT-A is a good marker for assessing anti-VEGF therapeutic response, especially the lesion size that has been demonstrated to decrease under anti-VEGF therapy.

OCT-A will be used in this study to assess the morphological response of patients to brolucizumab in terms of percentage change in CNV lesion area in the short term (i.e. at Week 12 just after loading doses) and in the long term (i.e. at Week 48 [12 months]), as well as changes in other OCT-A features up to Week 48.

The primary endpoint is the percentage change in CNV lesion area measured by OCT-A from Baseline to Week 12. The Week 12 time point has been selected as peak efficacy has been demonstrated in the pivotal trials of brolucizumab for this time point.

Anatomic parameters measured by OCT-A and SD-OCT

Anatomic parameters measured by OCT-A and by SD-OCT will be analyzed by a CRC. The main aim of the CRC analysis is to confirm anatomic features from OCT-A and SD-OCT images for the primary endpoint. The investigator will evaluate the OCT-A and SD-OCT images to assess the status of disease stability.

Disease activity criteria

Disease activity criteria will be assessed by the investigator based on whether nAMD is still active or has been re-activated. Guidance for the investigator is as follows (disease is active if at least one of the following criteria is observed by the investigator):

- BCVA decrease ≥ 5 letters from the best value since Baseline due to disease activity.
- Any significant increase in CRT (based on investigator assessment).
- Retinal hemorrhage.
- Intraretinal fluid or SRF due to disease activity (degenerative cysts allowed).
- Increase of sub-RPE fluid.

These criteria are for guidance only, the investigator may define disease activity based on his/her own assessment.

A patient who misses Week 16 will undergo the disease activity assessment at Week 20 as he/she would have done if the visit had not been missed. If, however, a patient misses any of the following disease activity assessment visits (Week 20, Week 32) then the patient will be assumed to have met the disease activity criterion at the missed visit and will be reassigned to a q8w regimen up to study exit.

If a patient misses Week 12, then the Week 8 values will be applied as the reference for disease activity assessments up to and including Week 44.

Fluorescein angiography: Fluorescein angiography (FA) is a diagnostic procedure that uses a special camera to record the blood flow in the RETINA – the light sensitive tissue at the back of the eye.

Color fundus photography (CFP): CFP is a diagnostic procedure that involves the use of a device known as a fundus camera to record colored images of the interior surface of the eye. The goal of this procedure is to monitor the presence of disorders and their change with time.

Fundus autofluorescence (FAF): Fundus autofluorescence imaging is an *in vivo* imaging method for metabolic mapping of naturally or pathologically occurring fluorophores of the ocular fundus.

Indocyanine green angiography (ICG): ICG is a diagnostic procedure that uses ICG dye to examine the blood flow in the choroid – the layer of blood vessels that lies underneath the retina. ICG is injected into a vein in the arm/hand. As the dye passes through the blood vessels of the eye, photographs are taken to record the blood flow.

Intraocular pressure (IOP): IOP is the fluid pressure of the eye. IOP is measured in millimeters of mercury (mmHg). Normal eye pressure is usually considered to be between 10 and 25 millimeters of mercury (mmHg).

Fundus examination: Fundus examination used to assess diagnose vitro-retinal diseases (such as retinal haemorrhage, vitreal haemorrhage, retinal tear and detachment), optic nerve defects and hereditary diseases.

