## 12 Data analysis and statistical methods

The primary efficacy and safety analysis will be based on the Week 12 data, i.e. data up to and including Week 12. This analysis will be performed once all patients have completed their Week 12 visit or prematurely discontinued the study before/on their Week 12 visit, while patients will continue to receive study treatment until their Week 40/Week 44 visit, dependent on their treatment regimen. The analysis of the data after the EOS/Week 48 visit will be performed once all patients have completed or prematurely discontinued the study.

The data will be analyzed by Novartis and/or a designated CRO. Any data analysis carried out independently by the investigator should be submitted to Novartis before publication or presentation.

It is planned that the data from all centers that participate in this protocol will be pooled, so that an adequate number of patients will be available for analysis.

In addition to the statistical methods outlined below, further details will be described in the Statistical Analysis Plan (SAP).

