### **12.5.2 Safety endpoints**

For all safety analyses, the Safety Set will be used.

The secondary safety endpoint of this study is as follows:

- Incidence of AEs (serious and non serious) reported in patients treated with brolocizumab.

Safety summaries (tables, figures) include only data from the on-treatment period with the exception of Baseline data, which will also be summarized where appropriate (e.g. change from Baseline summaries). In addition, a separate summary for death including on treatment and post treatment deaths will be provided. In particular, summary tables for adverse events of special interest (AESIs) will summarize only on-treatment events, with a start date during the on-treatment period (treatment-emergent AEs).

The on-treatment period lasts from the date of first administration of IVT injection of study treatment to 30 days after the date of the last actual administration of IVT injection of study treatment.

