2.9.1 Adverse events (AEs)

All information obtained on AEs will be displayed by patient. Summary tables for AEs will summarize only on-treatment events, with a start date during the on-treatment period (see Section 2.1.1) for definition of on-treatment period).

The count of treatment-emergent AEs, number (and percentage) of patients with treatment-emergent AEs (defined as events started after the first dose of study treatment or events present prior to start of study treatment but increased in severity based on PT) will be summarized in the following ways:

- By primary SOC and PT.
- By primary SOC, PT and maximum severity.

Separate summaries will be provided for study treatment related AEs, procedure related, death, SAEs and other significant AEs action taken leading to study treatment interruption & treatment withdrawn.

Adverse events will be summarized by presenting, the number and percentage of patients having any AE, having an AE in each primary SOC and having each individual AE (PT). Summaries will also be presented for AEs by severity. Summaries for AE will be presented for study treatment and procedure related to AEs. If a patient reported more than one AE with the same PT, the AE with the greatest severity will be presented. System organ classes will be presented in alphabetical order, PTs will be sorted within SOC in descending frequency of AEs. If a patients reported more than one AE within the same primary SOC, the patient will be counted only once with the greatest severity at the SOC level, where applicable. The AE will be presented in separate sections of ocular and non-ocular. For ocular then it will be presented by any eye, study eye and fellow eye.

For occurrence, the presence of at least one SAE / SAE suspected to be related to study treatment / non SAE has to be checked in a block e.g., among AEs in a \leq 1 day gap block, if at least one SAE is occurring, then one occurrence is calculated for that SAE.

The number of deaths resulting from SAEs suspected to be related to study treatment and SAEs irrespective of study treatment relationship will be provided by SOC and PT.

In addition, all treatment emergent AEs will also be listed.

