2.9.1.1 Adverse events of special interest / grouping of AEs

The number (%) of patients with AESIs will be summarized by standardized MedDRA query and PT. Listing will also be provided.

Case Retrieval Sheet (CRS) with the exact composition of the AE groupings is to be used to map reported AEs to the AESI groupings. This file may be updated (i.e.live document) based on review of accumulating trial data, and therefore the groupings are also subject to potential change. The most up-to-date version of the CRS will be used at the time of the analysis.

The number and percentage of patients having any AESI, AESI by SOC (confirmed by SRC) and PT will be presented.

The number and percentage of patients for AESI type along with incidence rate per patient and per 1000 injection will be provided. Incidence rate per patient is defined as number of patients in AESI type/total number of patients in safety analysis set and incidence rate per 1000 injection is define as (number of occurrence of AESI type/total number of injections)*1000.

The number and type of AESI will be plotted according to the time after last brolucizumab injection and time since first brolucizumab injection.

Summary statistics for change from baseline in BCVA after end date of AESI will be provided for each AESI type and change from baseline in BCVA will be plotted overall and for each type of AESI.

Patients demographics, baseline characteristics and medical history will be provided for AESI patient with safety set.

2.9.2 **Deaths**

A separate summary of deaths including on-treatment and post-treatment deaths will be provided.

All deaths in the clinical database will be listed with the investigator-reported principal cause. Deaths occurring after the first dose of study treatment until 30 days after the date of last treatment will be summarized. In addition, deaths occurring after the first dose of study treatment until the date of last treatment will also be summarized.

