2.14 Interim analysis

The analysis based on the Week 12 data, i.e. data up to and including Week 12 will be the primary (first) analysis for this study.

A second planned analysis of the data after the EOS/Week 48 visit will be performed once all patients have completed or prematurely discontinued the study.

3 Sample size calculation

The primary objective of the study is to evaluate the effect of brolucizumab on CNV lesion area as measured by OCT-A in nAMD patients starting treatment with brolucizumab. This will be evaluated by the percentage change in CNV lesion area measured by OCT-A from Baseline to Week 12. The sample size calculation is based on the hypothesis of a standard deviation of 35% for this reduction proportion (Miere et al 2018).

A sample size of 180 to 400 patients produces a 2-sided 95% CI with a distance from the mean to the limits ranges from 5.1 to 3.4 when the estimated standard deviation is 35.0 (nQuery Advisor version 7.0). Therefore, to have a precision of 5%, a sample size of 189 patients will be needed (Table 3-1).

To take into account a dropout rate and uninterpretable images of 10%, a total of 210 patients will be included.

Table 3-1 Confidence intervals for one mean numeric results for 2-sided confidence intervals with unknown standard deviation

Confidence Level	Sample Size (N)	Distance from Mean to Limits	Standard Deviation (S)
0.950	180	5.1	35.0
0.950	189	5.0	35.0

For business use only	Page 31 of 39	
	CRTH258AFR01	

Novartis		
SAP Addendum	Version	1.0

0.950	233	4.5	35.0
0.950	250	4.4	35.0
0.950	300	4.0	35.0
0.950	350	3.7	35.0
0.950	385	3.5	35.0
0.950	400	3.4	35.0

4 Change to protocol specified analyses

5 Appendix

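### AESI tables close 30 days after the last injection in the protocol (28 in the SAP's definition), so an event that starts later in an 8- or 12-week interval and ends treatment is not counted

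*SAP*

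**What the plan says.** **The window.** Protocol 12.5.2 runs the on-treatment period from the first injection "to 30 days after the date of the last actual administration of IVT injection of study treatment". It then says that "summary tables for adverse events of special interest (AESIs) will summarize only on-treatment events". SAP 2.1.1, with the same text in Amendment 2.0 and in the Addendum, has a shorter period: "The on-treatment period lasts from the date of first administration of study treatment to 28 days after the date of the last actual administration". SAP 2.9.1 uses that period: "Summary tables for AEs will summarize only on-treatment events, with a start date during the on-treatment period". For deaths, SAP 2.9.2 keeps the protocol's figure: "Deaths occurring after the first dose of study treatment until 30 days after the date of last treatment".

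**The AESI outputs.** SAP 2.9.1.1 adds a rate per patient and a rate per injection ("incidence rate per 1000 injection is define as (number of occurrence of AESI type/total number of injections)*1000"), plus plots by time since the first and the last injection. It does not mention the window.

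**Treatment.** After Week 8 the interval is 8 or 12 weeks (protocol 6.7.2). Signs of inflammation bar the injection (6.7.2 and 10), and confirmed inflammation, vasculitis or occlusion ends study treatment (6.1.4, 8.4.3, 9.1.1). AEs are then still collected to at least Week 48, and other anti-VEGF may be given in the study eye (9.1.1).

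**The analyses.** Protocol 12: "The primary efficacy and safety analysis will be based on the Week 12 data, i.e. data up to and including Week 12". SAP 2.14: "A second planned analysis of the data after the EOS/Week 48 visit will be performed once all patients" have completed or left the study.

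**The concern.** The window ends a fixed time after the last injection actually given, and the AESI itself decides which injection that is. An event that starts late in a maintenance interval cancels the next injection, which fixes the previous injection as the last. The window has then closed before the event began. An event with the same onset day that is followed by another injection is counted. Whether an AESI reaches the table thus depends on whether it stopped treatment, and the events that did are the ones dropped.

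These events are the safety question behind Amendments 2 to 4, and AE incidence is the trial's safety endpoint. A table that omits late, treatment-ending cases would make the AESI frequency look lower than the data collected show. Separately, an AE that starts on day 29 or 30 after the last injection is inside the period in the protocol and outside it in the SAP.

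**Working it through.** **Inputs.** Window w: 28 days (SAP 2.1.1) or 30 days (protocol 12.5.2). Intervals: 28 days in loading, then 56 or 84 days (protocol 6.7.2). End of study: Week 48 (protocol 3). Visit tolerance: 7 days either way (protocol 3 and 8). Planned patients: 210 (protocol 12.8.1).

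**1. The plan's own follow-up figure.** Days from last injection to end of study = (48 − week of last injection) × 7.
- Last injection at Week 44: 4 × 7 = 28 days, or 4 weeks.
- Last injection at Week 40: 8 × 7 = 56 days, or 8 weeks.

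Both agree with protocol Section 3.

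**2. Patient dosed as planned.** The period is continuous from the first injection, so only time after the last injection can be outside: max(0, follow-up − w).
- Week 44: max(0, 28 − 28) = 0 and max(0, 28 − 30) = 0 days.
- Week 40: 56 − 28 = 28 days (SAP) or 56 − 30 = 26 days (protocol).

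**3. Patient whose AESI ends treatment.** The injection that opened the interval becomes the last one. Days of that interval on which an onset would be excluded = max(0, interval − w).

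| Interval | SAP, w = 28 | Protocol, w = 30 |
|---|---|---|
| 28 days (loading) | 0 | 0 |
| 56 days | 56 − 28 = 28 (50%) | 56 − 30 = 26 (46%) |
| 84 days | 84 − 28 = 56 (67%) | 84 − 30 = 54 (64%) |

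**4. Example.** A patient shows no disease activity at Week 16. Inflammation starts around the Week 20 visit and that injection is withheld. The last injection is Week 8, so onset is on day (20 − 8) × 7 = 84. That is 84 − 28 = 56 days (SAP) or 84 − 30 = 54 days (protocol) past the cut-off, and the event is not tabulated. Had the Week 20 injection been given before the event was recognised, it would be counted.

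**5. Data up to Week 12.** On the planned schedule, Week 12 is 28 days after the Week 8 dose, which is inside both windows. Two routes to a loss remain.
- Slippage: a Week 8 dose 7 days early and a Week 12 visit 7 days late are (84 + 7) − (56 − 7) = 42 days apart. This leaves 42 − 28 = 14 days (SAP) or 42 − 30 = 12 days (protocol) outside.
- A stopped or missed loading dose: if only the Day 1 injection is given, the window closes 84 − 28 = 56 or 84 − 30 = 54 days before Week 12.

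**6. Scale.** One omitted AESI patient is 1/210 = 0.48 percentage points, if all 210 are in the Safety Set. If the rates inherit the window, the injection rate changes as follows. With six injections each (q12w), 210 × 6 = 1260 and one omitted event is 1000/1260 = 0.79 per 1000. With seven each (q8w from Week 16), 210 × 7 = 1470 and it is 1000/1470 = 0.68 per 1000. Both assume that all planned injections are given.

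**The case against.** - **The window does not reopen after every injection.** This stands. A reader might sum the uncovered part of every interval and infer that 168 of 336 days (50%) on q12w, or 140 (42%) on q8w, lie outside the period. The definitions do not support that: the period is continuous, and step 2 gives 0 days, or 28/26 days, for a patient dosed as planned. The summed figures only count the days on which a treatment-ending onset would be excluded.
- **SAP 2.9.1.1 may not apply the window.** This stands as an ambiguity. The section states no cut-off, the AESI code in SAP 5.4 has no date filter, and the treatment-emergent definition in 2.9.1 has no upper limit. It does not remove the concern, because protocol 12.5.2 restricts AESI tables by name and 2.9.1.1 sits under 2.9.1.
- **The events are not lost.** True: patients are told to report symptoms between visits, by-patient displays and listings are planned, and SAEs are reported to the last visit or 30 days after the last injection, whichever is later. But listings do not correct a table count.
- **An on-treatment count is a legitimate target.** It is, and after a switch to other anti-VEGF an onset is not clearly attributable to the study drug. A reader might infer that every exclusion biases the count downward; for onsets after such a switch the documents do not support that.
- **The 28/30-day difference may be recorded as a change.** SAP Section 4 shows no text in the copy available, so this cannot be ruled out.

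**Conclusion.** The point holds. Under protocol 12.5.2 as written, an AESI that starts more than 30 days into a maintenance interval and is followed by no further injection is left out of the AESI tables. With the SAP's definition the limit is 28 days. For onsets before any other anti-VEGF in the study eye, this biases the table count downward. The two AESI rates are affected only if 2.9.1.1 inherits the window; events then leave the numerators while all injections stay in the denominator.

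The loss falls mainly in the Week 48 analysis. A reader might infer that the Week 12 analysis is untouched; that is true only for patients who receive all three loading doses and keep to the visit schedule.

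The percentages in step 3 are shares of an interval, not of events. The documents give no distribution of onset times, so the number of AESIs lost cannot be derived. All day counts rest on nominal visit dates unless slippage is stated. This should be fixed, but it does not touch the primary efficacy endpoint.

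**What to change.** (a) Use one number of days for the on-treatment period in protocol 12.5.2 and SAP 2.1.1.

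(b) State in SAP 2.9.1.1 whether the window applies to the AESI counts, the two rates and the plots.

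(c) At the Week 48 analysis, keep the windowed table and report beside it the AESI counts and both rates for all onsets from first injection to the last study visit. Show onsets after other anti-VEGF in the study eye separately, and keep them out of the rate per 1000 injections.

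(d) Reconcile protocol 9.1.1, which collects AEs to at least Week 48 after treatment stops, with 10.1.1, which continues monitoring until 30 days after the last injection and may be meant as a minimum. Note under the all-onset table that late non-serious AEs may be incomplete.

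The cost is a few more tables and short text edits. No new data are needed, since protocol 9.1.1, Table 8-1 and 10.1.3 already provide for them. The downside is a reported AESI rate that may be slightly higher.
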